7.2.4 Day 11-14 for Subjects Still Hospitalized: SMT and Daily Evaluations

All subjects receive continued SMT.

Daily assessments include the following:

- Ordinal Scale assessment
- NEWS ([Appendix 2](#))
- Clinical features key symptoms: fever, cough, shortness of breath, fatigue, myalgia etc.
- Vital signs (temperature, systolic and diastolic blood pressure, pulse, respiratory rate)
- Record any supplemental oxygen administration (type, %, flow start/end date/time)
- Record details of mechanical ventilation parameters (start/end date/time)
- Record oxygen saturation (specify on or off oxygen supplementation)
- Record SAEs and TEAEs
- Record standard care concomitant medications

GRIFOLS Bioscience Industrial Group	Number	BIG-CL-PRT-000020	Version	4.0	Status	Effective	Effective Date	19-Jul-2021	Page	52 of 91
	GC2007 - A Multicenter, Randomized, Open-label Parallel Group Pilot Study to Evaluate Safety and Efficacy of High Dose Intravenous Immune Globulin (IVIG) plus Standard Medical Treatment (SMT) versus SMT alone in									

7.2.5 Day 15±1 day – All Subjects

Day 15±1 day may be performed at the study site or, if deemed appropriate, at an alternate site (e.g., subject's residence, local healthcare professional's site) under the care and supervision of trained healthcare personnel. If an in-person visit is unable to be conducted for Day 15, the study site will make a phone call to the subject to obtain as much information as possible remotely (e.g., Ordinal Scale, clinical features key symptoms, supplementation oxygen use, SAEs and TEAEs, concomitant medications).

Assessments include the following:

- Ordinal Scale assessment
- NEWS ([Appendix 2](#))
- Clinical features key symptoms: fever, cough, shortness of breath, fatigue, myalgia etc.
- Vital signs (temperature, systolic and diastolic blood pressure, pulse, respiratory rate)
- Record any supplemental oxygen administration (type, %, flow start/end date/time)
- Record details of mechanical ventilation parameters (start/end date/time)
- Record oxygen saturation (specify on or off oxygen supplementation)
- Assessment of ARDS (Berlin Criteria) ([Appendix 3](#))
- SOFA score ([Appendix 4](#))
- Respiratory sample for quantitative measurement of SARS-CoV-2 viral load by NAT or PCR (real-time RT-PCR) (obtained via nasopharyngeal swab)
- Sample for quantitative measurement of IgM and IgG antibodies to SARS-CoV-2 (store serum samples frozen at -70°C for later analysis at an external lab)
- Serum Chemistry (creatinine, albumin, ALT, total bilirubin, LDH)
- Ferritin (serum), D-dimer (plasma, sodium citrate tube), CRP (serum)
- Hematology absolute lymphocyte count and standard hematology (hemoglobin, hematocrit, platelet count, leukocyte count with differential)
- DAT
- Cytokine panel (IL-1 β , IL-10, IL-6, IL-8, IL-2, interferon γ , and TNF- α). Note: serum samples must be stored at -70°C for later analysis at a reference laboratory.
- Record SAEs and TEAEs
- Record standard care concomitant medications

GRIFOLS Bioscience Industrial Group	Number	Big-CL-PRT-000020	Version	4.0	Status	Effective	Effective Date	19-Jul-2021
	GC2007 - A Multicenter, Randomized, Open-label Parallel Group Pilot Study to Evaluate Safety and Efficacy of High Dose Intravenous Immune Globulin (IVIG) plus Standard Medical Treatment (SMT) versus SMT alone in							

7.2.6 Day 16-28 for Subjects Still Hospitalized: SMT and Daily Evaluations

All subjects receive continued SMT.

Daily assessments include the following:

- Ordinal Scale assessment
- NEWS ([Appendix 2](#))
- Clinical features key symptoms: fever, cough, shortness of breath, fatigue, myalgia etc.
- Vital signs (temperature, systolic and diastolic blood pressure, pulse, respiratory rate)
- Record any supplemental oxygen administration (type, %, flow start/end date/time)
- Record details of mechanical ventilation parameters (start/end date/time)
- Record oxygen saturation (specify on or off oxygen supplementation)
- Record SAEs and TEAEs
- Record standard care concomitant medications

7.2.7 Day 29±1 day – All Subjects

Day 29±1 day may be performed at the study site or, if deemed appropriate, at an alternate site (e.g., subject's residence, local healthcare professional's site) under the care and supervision of trained healthcare personnel. If an in-person visit is unable to be conducted for Day 29, the study site will make a phone call to the subject to obtain as much information as possible remotely (e.g., Ordinal Scale, clinical features key symptoms, supplementation oxygen use, SAEs and TEAEs, concomitant medications).

Assessments include the following:

- Ordinal Scale assessment
- NEWS ([Appendix 2](#))
- Clinical features key symptoms: fever, cough, shortness of breath, fatigue, myalgia etc.
- Vital signs (temperature, systolic and diastolic blood pressure, pulse, respiratory rate)
- Record any supplemental oxygen administration (type, %, flow start/end date/time)
- Record details of mechanical ventilation parameters (start/end date/time)
- Record oxygen saturation (specify on or off oxygen supplementation)
- Record hospital discharge date
- Record ICU discharge date
- Assessment of ARDS (Berlin Criteria) ([Appendix 3](#))
- SOFA score ([Appendix 4](#))

GRIFOLS	Number	BLG-CL-PRT-000020	Version	4.0	Status	Effective	19-Jul-2021
	GC2007 - A Multicenter, Randomized, Open-label Parallel Group Pilot Study to Evaluate Safety and Efficacy of High Dose Intravenous Immune Globulin (IVIG) plus Standard Medical Treatment (SMT) versus SMT alone in Bioscience Industrial Group					Page	54 of 91

- Respiratory sample for quantitative measurement of SARS-CoV-2 viral load by NAT or PCR (real-time RT-PCR) (obtained via nasopharyngeal swab)
- Sample for quantitative measurement of IgM and IgG antibodies to SARS-CoV-2 (store serum samples frozen at -70°C for later analysis at an external lab)
- Serum Chemistry (creatinine, albumin, ALT, total bilirubin, LDH)
- Ferritin (serum), D-dimer (plasma, sodium citrate tube), CRP (serum)
- Hematology: absolute lymphocyte count and standard hematology (hemoglobin, hematocrit, platelet count, leukocyte count with differential)
- DAT
- Cytokine panel (IL-1 β , IL-10, IL-6, IL-8, IL-2, interferon γ , and TNF- α). Note: serum samples must be stored at -70°C for later analysis at a reference laboratory.
- Record SAEs and TEAEs
- Record standard care concomitant medications

7.2.8 Day 60 \pm 2 days and Day 90 \pm 2 days Phone Checks – All Subjects

Phone Checks will be performed on Day 60 and Day 90:

- To confirm the subject's vital status (living or deceased)
- To record any hospital re-admissions
- To record any SAEs/non-serious AEs after the Day 29 final clinic visit

7.2.9 Description of Laboratory Tests and Procedures

[Table 7-1](#) provides a summary of the laboratory tests conducted for this study.

Table 7-1 Name, Description, and Location of Laboratory Tests and Procedures

Test Panel ^a		Description	Location
Hematology		Absolute lymphocyte count; Basic hematology: Hemoglobin, hematocrit, platelets, white blood cell (WBC) count with differential	Local
Chemistry		Creatinine, albumin, alanine aminotransferase (ALT), total bilirubin, lactate dehydrogenase (LDH)	Local
Markers of inflammation		C-reactive protein (CRP), D-dimer, ferritin	Local
Direct Coombs		direct antiglobulin test (DAT)	Local
Cytokine panel		Cytokine panel includes IL-1 β , IL-10, IL-6, IL-8, IL-2, interferon γ , and tumor necrosis factor- α (TNF- α). Note: serum samples must be stored at -70°C for later analysis at a reference laboratory.	Central
Quantitative measurement of SARS-CoV-2 viral load by NAT or PCR (RT-PCR)		Quantitative NAT or PCR (real-time RT-PCR) in respiratory samples (obtained via nasopharyngeal swab)	Central
Quantitative measurement of IgM and IgG antibodies to SARS-CoV-2		Quantitative IgM and IgG antibody levels by ELISA, IFA, or other assay methodology (store serum samples frozen at -70°C for later analysis at an external lab)	Central

8 ASSESSMENT OF SAFETY

8.1 Safety Parameters

The safety and tolerability of Gamunex-C in subjects with COVID-19 will be evaluated in this study. Safety endpoints will include:

- Cumulative incidence of treatment-emergent SAEs and potentially related SAEs through Day 90 Phone Check
- Cumulative incidence of Grade 3-5 TEAEs and potentially related severe TEAEs through Day 29 as defined in the CTCAE, US Department of Health and Human Services, NIH, and NCI
- Cumulative incidence of all TEAEs and potentially related TEAEs through Day 29

In this clinical study, disease progression is defined as the worsening of a subject's condition attributable to the disease for which the investigational product is being studied. It may be an increase in the severity of the targeted disease and/or increases in the symptoms of the targeted disease. Anticipated symptoms of COVID-19 include fever, cough, hypoxia, dyspnea, hemoptysis, myalgia, fatigue, pharyngitis which may develop at any time during the course of the disease. The development of COVID-19 symptoms during the clinical study should not be recorded as individual TEAEs, unless there is evidence suggesting a causal relationship between IVIG and the TEAE.

GRIFOLS Bioscience Industrial Group	Number	BLG-CL-PLT-000020	Version	4.0	Status	Effective	Effective Date	19-Jul-2021
	GC2007 - A Multicenter, Randomized, Open-label Parallel Group Pilot Study to Evaluate Safety and Efficacy of High Dose Intravenous Immune Globulin (IVIG) plus Standard Medical Treatment (SMT) versus SMT alone in						Page	56 of 91

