6.2.2 Prohibited Concomitant Medications during the Study

Administration of other commercial IVIG products during study is not allowed.

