After all Screen/Baseline assessments are complete subjects may be randomized.

Subjects in the combination arm may receive the first infusion of Gamunex-C on Screen/Baseline and Randomized Treatment visit (Day 1) if eligibility criteria are met, and all pre-infusion assessments are performed. Subjects in the combination arm will receive a total of 2 g/kg Gamunex-C in divided doses. At the prerogative of the Principal Investigator the 2 g/kg dose may be divided into 4 days (500 mg/kg/day) or 5 consecutive days (400 mg/kg/day).

Vital signs will be monitored during Gamunex-C infusion. Vital signs will be measured within 1 hour prior to the start of Gamunex-C infusion, 30 minutes after the start of infusion, and hourly through the end of Gamunex-C infusion. If the systolic blood pressure measured within 1 hour prior to the start of Gamunex-C infusion is > 160 mm Hg, then measures to lower blood pressure below this threshold should be administered and documented prior to commencing Gamunex-C infusion. To commence the Gamunex-C infusion, the systolic blood pressure must be < 160 mm Hg.

7.2.3 SMT, Randomized IVIG Treatment, Daily Evaluations (Days 2 through 10 inclusive) and Additional Day 5±1 Day Assessments

All subjects receive continued SMT. Subjects randomized to IVIG plus SMT will receive the remainder of the net 2 g/kg dose in divided doses at the Principal Investigator's prerogative on consecutive days through Day 4 (500 mg/kg/day) or through Day 5 (400 mg/kg/day) to achieve the total dose of 2 g/kg body weight. Subjects receiving Gamunex-C infusions will have vital signs measured within 1 hour prior to the start of each Gamunex-C infusion, 30 minutes after the start of infusion, and hourly through the end of Gamunex-C infusion. If the systolic blood pressure measured within 1 hour prior to the start of Gamunex-C infusion is > 160 mm Hg, then measures to lower blood pressure below this threshold should be administered and documented prior to commencing Gamunex-C infusion. To commence the Gamunex-C infusion, the systolic blood pressure must be < 160 mm Hg.

Daily assessments include the following:

- Ordinal Scale assessment
- NEWS ([Appendix 2](#))
- Clinical features key symptoms: fever, cough, shortness of breath, fatigue, myalgia etc.
- Vital signs (temperature, systolic and diastolic blood pressure, pulse, respiratory rate)
- Record any supplemental oxygen administration (type, %, flow start/end date/time)

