8.3.1 Warnings/Precautions

True hypersensitivity reactions from IVIG administration are rare. They can occur in subjects with anti-IgA antibodies. Rarely, human normal immunoglobulin can induce a fall in blood pressure with anaphylactic reaction, even in subjects who had tolerated previous treatment with human normal immunoglobulin.

There is clinical evidence of an association between IVIG administration and thromboembolic events such as myocardial infarction, cerebral vascular accident (including stroke), PE, and DVT that is assumed to be related to a relative increase in blood viscosity through the high influx of immunoglobulin in at-risk subjects. In subjects at risk for thromboembolic adverse reactions, IVIG products should be administered at the minimum rate of infusion and dose practicable.

Cases of acute renal failure have been reported in subjects receiving IVIG therapy. In most cases, risk factors have been identified, such as pre-existing renal insufficiency, diabetes mellitus, hypovolemia, overweight, concomitant nephrotoxic medicinal products, or age over 65. In case of renal impairment, IVIG discontinuation should be considered. While these reports of renal dysfunction and acute renal failure have been associated with the use of many of the licensed IVIG products containing various excipients such as sucrose, glucose, and maltose, those containing sucrose as a stabilizer accounted for a disproportionate share of the total number. In subjects at risk, the use of IVIG products that do not contain these excipients may be considered. Gamunex-C *does not* contain sucrose, maltose, or glucose.

AMS has been reported to occur in association with IVIG treatment. The syndrome usually begins within several hours to 2 days following IVIG treatment.

Gamunex-C may contain blood group antibodies which may act as hemolysins and induce in vivo coating of red blood cells with immunoglobulin, causing a positive DAT and, rarely, hemolysis. Hemolytic anemia can develop subsequent to IVIG therapy due to enhanced red blood cells sequestration. IVIG recipients should be monitored for clinical signs and symptoms of hemolysis. If these are present after IVIG infusion, perform appropriate confirmatory laboratory testing.

In subjects receiving IVIG, there have been some reports of acute non-cardiogenic pulmonary oedema (Transfusion Related Acute Lung Injury [TRALI]). TRALI is characterized by severe hypoxia, dyspnoea, tachypnoea, cyanosis, fever and hypotension.

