8.3.8 Adverse Event Documentation

All AEs and SAEs occurring on Day 1 through the Day 29 (± 1 day)/Final Visit must be fully recorded in the subject’s medical record and CRF, and SAE form (if serious).

At the time of the Day 60 (± 2 days) and Day 90 (± 2 days) Phone Checks any additional SAEs/non-serious AEs will also be collected and recorded.

It is the responsibility of the investigator to ensure that AEs are appropriately recorded.

AEs will be collected through directly observed events or spontaneously volunteered by the subject. Clearly related signs, symptoms and abnormal diagnostic procedures should preferably be grouped together and recorded as a single diagnosis or syndrome wherever possible.

The following variables must be recorded:

- The verbatim term (a diagnosis is preferred)
- Date/time of onset
- Date/time of resolution
- Severity (mild, moderate, severe [Grade 3 to Grade 5])
- Causality (unrelated, possibly related, definitely related)*
- Seriousness (yes, no)
- Action taken (with regard to IP)
- Other action (to treat the event)
- Outcome and sequel (follow-up on AE)

*Causality assessment will be made only when the AE occurs after the subject has initiated at least one infusion of the IP. An AE occurring before subject’s exposure to IP will be always labeled as “unrelated”.

GRIFOLS Bioscience Industrial Group	Number	BlG-CL-PRT-000020	Version	4.0	Status	Effective	Effective Date	19-Jul-2021	Page	61 of 91
	GC2007 - A Multicenter, Randomized, Open-label Parallel Group Pilot Study to Evaluate Safety and Efficacy of High Dose Intravenous Immune Globulin (IVIG) plus Standard Medical Treatment (SMT) versus SMT alone in									

For AEs that occur during infusions, the infusion rate in effect at the time of onset of the AE, the time of onset of the AE and the time of AE change materially in intensity and/or resolve will be captured.

In addition to the investigator's own description of the AE, each AE will be encoded according to the Medical Dictionary for Regulatory Activities (MedDRA).

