### **2.2.4 Safety Endpoints**

The safety endpoints include:

- Cumulative incidence of treatment-emergent serious adverse events (SAEs) and potentially related SAEs through Day 90 Phone Check
- Cumulative incidence of Grade 3-5 treatment-emergent adverse events (TEAEs) and potentially related severe TEAEs through Day 29 as defined in the Common terminology Criteria for Adverse Events (CTCAE), US Department of Health and Human Services, National Institutes of Health (NIH), and National Cancer Institute (NCI)
- Cumulative incidence of all TEAEs and potentially related TEAEs through Day 29

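### For the listed COVID-19 symptoms only IVIG-treated subjects can meet the condition for a TEAE, so the by-arm TEAE rates for those terms reflect the attribution rule

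*Protocol*

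**What the plan says.** Protocol 8.1 lists the symptoms: "Anticipated symptoms of COVID-19 include fever, cough, hypoxia, dyspnea, hemoptysis, myalgia, fatigue, pharyngitis". When they develop during the study they "should not be recorded as individual TEAEs, unless there is evidence suggesting a causal relationship between IVIG and the TEAE". The same rule stands in the synopsis, in 4.1.4, inside the AE definition in 8.3.3.1, and in footnote d of both the protocol and the SAP schedules.

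Protocol 8.3.8 determines who can meet the exception: "Causality assessment will be made only when the AE occurs after the subject has initiated at least one infusion of the IP". An event before "exposure to IP will be always labeled as" unrelated. Protocol 6.2.2 adds: "Administration of other commercial IVIG products during study is not allowed". Treatment is open-label (Protocol 4.3.3).

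The safety objective compares IVIG plus SMT with SMT alone (Protocol 3.2). One safety endpoint is "Cumulative incidence of all TEAEs and potentially related TEAEs through Day 29" (SAP 2.2.4), and another is Grade 3-5 TEAEs. SAP 7.2.5 plans any-TEAE, Grade 3 or higher, and system organ class and preferred term tables; SAP 4 has summaries given by treatment group. SAP 7 plans no formal safety test.

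**The concern.** Leaving expected disease symptoms out of AE reporting is an ordinary convention when it applies to every arm. Here the exception can be met in one arm only. A reader of the TEAE tables would take fever or dyspnea under IVIG, against none under SMT alone, as a treatment difference, and nothing in the SAP says that these terms were collected differently.

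The rule can also hide harm. Fever is among the adverse reactions to IVIG named in Protocol 2.2, and Protocol 8.3.1 warns that "TRALI is characterized by severe hypoxia, dyspnoea, tachypnoea, cyanosis, fever and hypotension". Hypoxia, dyspnea and fever are therefore both excluded COVID-19 symptoms and signs of a listed IVIG risk. If the investigator, who knows the treatment, puts such an event down to COVID-19, it is not entered as an individual TEAE, and there is no control rate to set the IVIG rate against.

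**Working it through.** The documents state no expected TEAE rate and no safety power, so there is no planned figure to reproduce. I followed the rule arm by arm and then sized the effect under assumptions.

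**Step 1: can each arm meet the exception?**

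| | IVIG plus SMT | SMT alone |
|---|---|---|
| Receives the investigational product | Yes | No |
| Causality assessed (Protocol 8.3.8) | After the first infusion starts | Never |
| Listed symptom treated as COVID-19 | Not a TEAE | Not a TEAE |
| Listed symptom suspected to be due to IVIG | TEAE | Cannot arise |

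The exception asks for nearly what Protocol 8.3.4 requires for a possibly related event. A symptom admitted under it is therefore already an adverse drug reaction in SAP 7.2.5. For these terms, all TEAEs reduce to potentially related TEAEs, although the two are listed as separate measures. SAP 7.2.1 defines treatment emergence by randomization date, which is neutral between arms, but it cannot restore events that were never entered.

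**Step 2: recorded rate for the symptom terms.** Let q be the true proportion of subjects with a listed symptom and a the probability that it is attributed to IVIG. The recorded rate is q × a under IVIG and 0 under SMT alone. From the documents: about 100 subjects randomized 1:1, so about n = 50 per arm. Assumed: q from 0.2 to 0.8 and a from 0.05 to 0.30, with q equal in both arms.

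| q | a | q × a | Expected IVIG subjects, 50 × q × a | SMT alone | Chance of at least one under IVIG, 1 − (1 − q × a)^50 |
|---|---|---|---|---|---|
| 0.2 | 0.05 | 1% | 0.5 | 0 | 0.40 |
| 0.5 | 0.10 | 5% | 2.5 | 0 | 0.92 |
| 0.5 | 0.20 | 10% | 5 | 0 | 0.995 |
| 0.8 | 0.30 | 24% | 12 | 0 | above 0.99 |

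**Step 3: what happens to a true difference.** The recorded difference is q(IVIG) × a − 0, and the SMT incidence drops out. With a = 0.10, true rates of 0.8 and 0.8 give 8% against 0%; so do 0.8 and 0.5. If nothing is attributed (a = 0), every pair of true rates gives 0% against 0%.

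**Step 4: effect on the any-TEAE rate.** Let b be the background rate of other TEAEs, assumed equal in both arms and independent of the symptoms. The IVIG rate is 1 − (1 − b)(1 − q × a), so the spurious excess is (1 − b) × q × a.

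| b | q × a = 0.01 | q × a = 0.05 | q × a = 0.24 |
|---|---|---|---|
| 0.5 | 0.5 points | 2.5 points | 12 points |
| 0.9 | 0.1 points | 0.5 points | 2.4 points |

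**Step 5: one rule for both arms.** If the listed terms are excluded in both arms, equal true incidence gives 0 − 0 = 0; if they are recorded in both, q − q = 0.

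**The case against.** The strongest reply is that the information is not lost. "Clinical features key symptoms: fever, cough, shortness of breath, fatigue, myalgia etc" are collected in both arms whatever the attribution, and SAP 7.5 tabulates them by treatment group. SAP 6.2 also summarises oxygen duration, mechanical ventilation, the ordinal scale, ARDS, SOFA and NEWS by arm, and NEWS includes saturation and respiratory rate. A reader might infer that an unattributed excess of hypoxia or dyspnea would be invisible in the trial; the documents do not support that. It would be missing from the TEAE tables. The cover elsewhere is partial: the named key symptoms omit hypoxia, hemoptysis and pharyngitis, SAP 6.2 only lists saturation values, and none of these records is CTCAE-graded.

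A reader might also infer that serious events are biased in the same way. Protocol 8.3.9 requires SAEs to be reported regardless of attribution, and Protocol 13.1 requires all AEs and SAEs to be recorded. Set against Protocol 8.1, that is an ambiguity to reconcile, not a demonstrated bias.

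Three further points stand. No safety test is planned and no numerical stopping criterion in Protocol 8.5 uses a between-arm difference, so no planned decision rests on the asymmetry. Protocol 8.3.8 prefers a diagnosis to separate symptoms, so recognised TRALI would be entered as such; unrecognised cases would not. SAP 7.2.5 already tabulates related TEAEs by preferred term, so a careful reader could identify the attributed cases, but would have to know the rule to do so.

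**Conclusion.** The point holds for a defined set of terms and a defined set of tables. Following the plan exactly gives a one-sided count of the listed symptoms in the all-TEAE and Grade 3 or higher tables. The direction needs no assumed rate: with equal true incidence, any attribution to IVIG produces an excess under IVIG. The potentially related endpoints can only be counted under IVIG in any case and are not the issue. A symptom with a clear cause other than COVID-19 may be recordable in either arm; the 0% applies to symptoms handled as COVID-19.

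The size cannot be derived from the documents. The range of 1% to 24% against 0% rests on assumed q and a and concerns the symptom terms only. It would be wrong to infer that the any-TEAE comparison is distorted by as much: at an assumed background of 90% the excess is 0.1 to 2.4 points, rising to 12 points at 50% with the most extreme inputs. The effect is on descriptive incidence, not on a planned p-value. This is a cheap improvement to the safety display.

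**What to change.** In SAP 7.2.5:

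1. Keep the planned TEAE tables, with a footnote that the listed COVID-19 symptoms become TEAEs only on suspected IVIG causality and so cannot enter from SMT-alone subjects.
2. Add any-TEAE, Grade 3 or higher, and system organ class and preferred term tables that exclude the listed terms in both arms.
3. Show the IVIG-attributed cases of those terms separately.
4. Base the between-arm comparison of these symptoms on the SAP 7.5 clinical features and the oxygen and saturation records, and summarise saturation by arm instead of only listing it.

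In the protocol, reconcile 8.1 (and its repeats) with 8.3.9 and 13.1 on whether serious symptom events are exempt from the attribution condition.

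The SAP changes use data already collected and cost one extra table set; the reconciliation is a wording change. Two further steps are not recommended. Taking attributed reactions out of the main tables would remove suspected IVIG reactions from the primary safety display. Changing how Grade 3 or higher symptoms are recorded at this stage would leave earlier and later subjects recorded under different rules.
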